### **5.2.1 Dose Selection/Modification**

#### **5.2.1.1 Dose Selection**

Investigator / sub-investigator will select the initial formulation according to the subject's condition. Subjects who have central intravenous catheter or are judged to be able to administer via central venous at the timing of randomization by investigator will start with MK-5592 IV solution or voriconazole IV. Administration of MK-5592 IV solution or

voriconazole IV need to be considered for the subjects who present with or are expected to have intolerance to oral study drug administration (e.g. conditions which may interfere with oral intake or absorption of study drug such as vomiting or oral mucosal disorders). Subjects who are judged to be able to take the tablet at the timing of randomization by investigator will start with MK-5592 solid oral tablet or voriconazole tablet.

After the initiation of the IV formulation, transition from IV to oral therapy on or after Day 9 may occur when the subject is considered clinically stable and able to take oral administration by investigator's discretion. When switching the formulation, the investigator must evaluate the overall response. In case that subject who started using oral formulation cannot continue to receive the oral formulation during the treatment, investigator must evaluate the overall response at that time and conduct the discontinuation procedure. Data gathered on the day of switching formulation or preceding day can be used as an overall response at the switching formulation [However, if the subject is a patient with zygomycosis and joins the extension period, the switch of the formulation(iv↔tablet) could be done based on the subject's condition but dose modification of MK-5592 must not be allowed and the investigator does not need to evaluate the overall response at the timing of switching the formulation].

For subjects with estimated creatinine clearance of 30~50 mL/min who receive IV formulation of MK-5592 or voriconazole, serum creatinine is carefully monitored. If serum creatinine is increased, switching to the oral therapy should be considered. Worsening of renal impairment may occur due to accumulation of sulfobutylether-beta-cyclodextrine sodium.

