### 5.2.1.3 Treatment Duration

As a general rule, the treatment duration of all diseases is 84 days (77-84 days with considering the final treatment allowance). [However, for the subjects with zygomycosis, restart of the study therapy after finishing 84 day maximum treatment period or extension of treatment period could be done under the extension period with the prior approval from the Sponsor and obtaining the signing of a new informed consent from the only subject who have responded to the study therapy without intolerant toxicity if the investigator thinks that continuation of MK-5592 therapy would benefit the subjects with ample consideration of the MK-5592 profile and no alternative treatment in Japan (e.g. failure or intolerant to amphotericin B formulation). In addition to the above, in case of restart of the study therapy after the finishing 84 days, it can be done for the only subjects with same zygomycosis episode from the main study therapy (not new episode). The switch of the formulation (iv $\leftrightarrow$ tablet) could be done based on the subject's condition during the extension period but dose modification of MK-5592 must not be allowed. However, the study therapy must be discontinued when MK-5592 is marketed or the development of MK-5592 is discontinued in Japan. As a general rule, study medication information and adverse events are recorded (routine safety laboratory should be also monitored and recorded in the source document) during the study treatment over 84 days but refer to the specific procedure relating this matter including the details of information that should be recorded in CRF.] However, the treatment may be completed earlier if the subject does not need the therapy any longer by the investigator's discretion (e.g. cure of the target infection). The therapy may also be discontinued prematurely if the investigator decides that the patient is not capable of receiving further therapy (e.g. adverse event) although the investigator feels that the patient requires further treatment for the condition under study (refer to section 5.8 for discontinuation criteria).

In the event that the additional work-up does not result in a proven or probable IA diagnosis within 7 days of randomization, subjects should continue participation in the trial with possible IA.

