11. At the switching formulation (from IV to PO), investigator must evaluate the overall response (including clinical response, radiological response, and mycological response). Data conducted on the day of switching formulation or preceding day can be used as an overall response at the switching formulation. In case that subject who started using oral formulation cannot continue to receive the oral formulation during the treatment, investigator must evaluate the overall response at that time and conduct the discontinuation procedure [However, if the subject is a patient with zygomycosis and joins the extension period, the switch of the formulation(iv↔tablet) could be done based on the subject's condition but dose modification of MK-5592 must not be allowed and the investigator does not need to evaluate the overall response at the timing of switching the formulation].
12. Weight measurement and Treatment Allocation may be conducted between Day -1 and Day 1. Treatment allocation and weight measurement should be conducted on the same date. Weight used for treatment allocation should be considered as basis of the dosing calculation. When conducting the Visit 2 weight measurement on Day -1, weight measurement does not need to be repeated on Day 1.
13. As a general rule, treatment duration of all disease is 84 days (77-84 days with considering the treatment allowance). At the EOT (completion and discontinuation) visit before the transition to the extension period, procedure other than dose administration should be conducted within EOT +2 days. At the end of treatment or discontinuation, procedure at EOT should be conducted before starting other systemic antifungal therapy[However, if the subject is a patient with zygomycosis and joins the extension period, procedure at visit 12/EOT does not need to be conducted at the last dose of MK-5592 therapy in the extension period].
14. Informed Consent could be obtained prior 28 days of Day 1.
15. Urine pregnancy testing can be conducted. Even though urine pregnancy testing is conducted, serum pregnancy testing should be conducted as a screening testing.

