### **8.2.10.2 Oral Therapy**

A day within the study will be considered an “On-Therapy” day if the patient takes the required number of tablets. For a patient who is followed for the entire study period, the “Number of Days Should be on Therapy” is the total number of days from randomization to the last scheduled day for treatment administration for that patient. For a patient who discontinued from the study permanently, the “Number of Days Should be on Therapy” is the total number of days from randomization to the earlier/later date of the last dose of study medication.

For each patient, percent compliance will then be calculated using the following formula:

$$\text{Percent Compliance} = \frac{\text{Number of Days on Therapy}}{\text{Number of Days Should be on Therapy}} \times 100.$$

Summary statistics will be provided on percent compliance by treatment group for the FAS and ASaT.

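### The oral compliance formula counts only tablet days but divides by all days since randomisation, so an IV-to-oral switcher who misses no dose scores below 100%

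*Combined protocol and SAP*

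**What the plan says.** Section 8.2.10.2 (Oral Therapy) defines the numerator by tablets alone: "A day within the study will be considered an “On-Therapy” day if the patient takes the required number of tablets". For a patient followed for the whole study period, the number of days due "is the total number of days from randomization to the last scheduled day for treatment administration for that patient". When a patient stops permanently, it "is the total number of days from randomization to the earlier/later date of the last dose of study medication". The ratio is not restricted to subjects treated only by mouth: "For each patient, percent compliance will then be calculated using the following formula". On reporting: "Summary statistics will be provided on percent compliance by treatment group for the FAS and ASaT".

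Switchers are an expected group. Section 5.2.1.1 says that "transition from IV to oral therapy on or after Day 9 may occur", at the investigator's discretion. Sections 8.1.1 and 8.2.5.1.1 pool switchers with the other subjects of their arm, and Section 8.2.8 lists switch as a route subgroup.

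Section 8.2.10.1 (IV Route) gives the same ratio without defining either of its terms. It also reports separately the subjects with missed, incorrect, unscheduled or too-fast infusions. Section 8.2.11 summarises exposure through the Number of Days on Therapy, a term that only Section 8.2.10.2 defines at the level of a day.

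On timing, footnote 12 of the Trial Flow Chart states: "Weight measurement and Treatment Allocation may be conducted between Day -1 and Day 1". Section 5.2.1.3 states that "the treatment duration of all diseases is 84 days (77-84 days with considering the final treatment allowance").

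**The concern.** For a switcher, the two halves of the ratio cover different periods. An infusion day cannot count as a tablet day, yet it is counted as a day on which therapy was due. The shortfall measures how long the subject was on infusions, not how many doses were missed, and it grows with every day the switch is delayed.

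At stake is whether the compliance table can be read as adherence. If the tablet-only definition is also used in Section 8.2.11, treatment duration would be under-reported for the same subjects. That matters somewhat more in a trial whose primary objective is safety.

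Two smaller defects sit in the same paragraph. The count starts at randomisation, which may fall on the day before the first dose. The rule for subjects who discontinue still contains an unresolved choice of date (earlier/later), so it cannot be programmed as written.

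**Working it through.** The plan states no compliance figure, so there is none to reproduce. The check applies the formula in Section 8.2.10.2 to a subject who misses no dose.

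**Inputs**
- D, days of treatment: 84, with 77 as the lower end of the allowance (Section 5.2.1.3).
- s, first tablet day: 9 or later (Section 5.2.1.1).
- Allocation on Day 1, both end days counted.

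**Formula.** Tablet days = D − s + 1 and days due = D, so oral compliance = 100 × (D − s + 1)/D.

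| First tablet | Tablet days / days due, D = 84 | Oral compliance |
|---|---|---|
| Day 9 | 76/84 | 90.5% |
| Day 14 | 71/84 | 84.5% |
| Day 28 | 57/84 | 67.9% |
| Day 42 | 43/84 | 51.2% |
| Day 56 | 29/84 | 34.5% |

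The value is below 100% for every s from 9 to 84 and falls strictly as s rises, so 90.5% is the ceiling for a switcher over 84 days. With D = 77, the Day 9, 28 and 42 values are 69/77 = 89.6%, 50/77 = 64.9% and 36/77 = 46.8%.

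**After repair.** The same subjects score 100% at every switch day in either of two ways:
- Either route counted: ((s − 1) + (D − s + 1))/D = D/D.
- Oral denominator started at the first tablet: (D − s + 1)/(D − s + 1).

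**Exposure.** If Section 8.2.11 takes over the tablet-only day, a subject treated for 84 days with first tablet on Day 28 contributes 57 days on therapy instead of 84.

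**Start at randomisation.** With allocation on Day −1 and first dose on Day 1, one undosed day is added. A subject on tablets throughout then scores 84/85 = 98.8%, and a Day 9 switcher 76/85 = 89.4%.

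**Arm level.** The documents do not give the share f of switchers. Assume 10% to 50%, all switching on the same day, with every other subject scored at 100%. The arm mean is 100 × [(1 − f) + f × (84 − s + 1)/84].
- First tablet Day 9: 99.0% to 95.2%.
- First tablet Day 15: 98.3% to 91.7%.
- First tablet Day 29: 96.7% to 83.3%.

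**IV route, conditional.** If the undefined denominator in Section 8.2.10.1 were also all 84 days, a Day 9 switcher would score 8/84 = 9.5% and a Day 42 switcher 41/84 = 48.8%. These values rest on an assumed denominator and show only that the section is open to this reading.

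**The case against.** The best defence is that the plan is silent on switchers, not wrong about them. Section 8.2.10 introduces both routes together and says that injection volumes and remaining tablets will be used to calculate patient compliance. On an infusion day the required number of tablets is arguably zero, so a sensible programmer might count that day as on therapy. This reading is strained. Section 8.2.10.2 defines the day by tablets taken, applies the ratio to each patient, and nowhere says that an infusion day qualifies. A convention that rescues the formula has to be written down. The start at randomisation and the unresolved end date remain under any reading.

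Other parts of the defence stand, because a reader might infer more than the documents support:

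- *Switchers would be classed as non-compliant.* The plan sets no cut-off and reports summary statistics only, so the result is a value below 100%. Even under an assumed 80% limit, which is not in the documents, only a first tablet on Day 18 or later would fail over 84 days (Day 17: 68/84 = 81.0%; Day 18: 67/84 = 79.8%).
- *The low IV percentages are planned results.* They depend on a denominator that Section 8.2.10.1 does not define, and infusion deviations are tabulated separately.
- *The artefact will separate the arms.* Section 5.2.1.1 applies one switch rule to both arms. Switch timing is an open-label decision, and Table 14 specifies central intravenous use for MK-5592 but only intravenous use for voriconazole, so a difference is conceivable. Nothing in the documents shows one.
- *Efficacy or safety estimates are affected.* The FAS, ITT, Per-Protocol and ASaT definitions in Section 8.2.4 do not use percent compliance, nor does any response rate, adverse-event comparison or sample-size figure.

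The Day −1 start matters little in practice. Section 5.2 asks for treatment to begin on the day of randomisation or as near to it as possible, and an 84-day tablet completer loses only 1.2 percentage points. A larger loss needs a very early stop: 3/4 = 75% for a subject allocated on Day −1 whose last dose is on Day 3.

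**Conclusion.** The point holds. Followed literally, Section 8.2.10.2 gives a switcher with no missed dose a compliance of at most 90.5% over 84 days, falling to 67.9% for a first tablet on Day 28 and 51.2% on Day 42. These figures assume allocation on Day 1, inclusive day counts and infusion days not counted as on therapy, as the text defines it.

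The consequence is limited to the descriptive compliance summary and, if the definition carries over, the exposure summary. The size at arm level cannot be fixed without the share and timing of switches, and a between-arm difference remains a possibility only. It is worth correcting because a stated rule gives a wrong number for a group the plan expects. It does not threaten the trial's main results.

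**What to change.** Compute one compliance value per subject. The numerator is the number of days fully dosed by the route in use, infusion or tablet. The denominator runs from first dose to the last scheduled treatment day for subjects followed for the entire study period, and from first dose to the actual last dose for subjects who discontinue. That replaces the earlier/later wording and removes the start at randomisation. The text should also say which end date applies when treatment is completed early because it is no longer needed, as Section 5.2.1.3 allows.

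Use the same either-route definition of a day on therapy in Section 8.2.11.

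If route-specific values are kept, start the oral denominator at the first tablet day, end the IV denominator at the last infusion day, and define both terms of the ratio in Section 8.2.10.1.

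The cost is SAP wording and one derivation. Infusion times, tablet diaries and missed doses are already recorded, so no new data are needed.

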### **8.2.11 Extent of Exposure**

The extent to exposure to study treatment will be evaluated by summary statistics (N, mean median, standard deviation) and frequencies for the “Number of Days on Therapy” by treatment group.

## **9.0 LABELING, PACKAGING, STORAGE AND RETURN OF CLINICAL SUPPLIES**

### **9.1 Investigational Product**

The investigator shall take responsibility for and shall take all steps to maintain appropriate records and ensure appropriate supply, storage, handling, distribution and usage of investigational product in accordance with the protocol and any applicable laws and regulations.

Clinical Supplies will be provided by the Sponsor as summarized in [Table 29](#).

Table 29 Product Descriptions

Product Name & Potency	Dosage Form
MK-5592 18 mg/mL, 300 mg/vial	IV solution for injection
MK-5592, 100 mg	Tablet
Voriconazole, 200 mg/vial	Lyophilized Powder
Voriconazole, 50 mg	Tablet

## **9.2 Packaging and Labeling Information**

Clinical supplies will be affixed with a clinical label in accordance with regulatory requirements.

MK-5592 IV solution will be supplied as kits containing one vial. MK-5592 tablets will be supplied as bottles containing 30 tablets. No kitting is required. Voriconazole Lyophilized Powder will be supplied as kits containing ten vials. Voriconazole tablets will be supplied as kits containing 50 tablets in PTP sheets. All of clinical supplies will be supplied as open label.

## **9.3 Clinical Supplies Disclosure**

This trial is open-label; therefore, the subject, the trial site personnel, the Sponsor and/or designee are not blinded to treatment. Drug identity (name, strength) is included in the label text; random code/disclosure envelopes or lists are not provided.

## **9.4 Storage and Handling Requirements**

Clinical supplies must be stored in a secure, limited-access location under the storage conditions specified on the label.

Receipt and dispensing of trial medication must be recorded by an authorized person at the trial site.

Clinical supplies may not be used for any purpose other than that stated in the protocol.

## **9.5 Returns and Reconciliation**

The investigator is responsible for keeping accurate records of the clinical supplies received from the Sponsor or designee, the amount dispensed to and returned by the subjects and the amount remaining at the conclusion of the trial.

For all trial sites, the local country Sponsor personnel or designee will provide appropriate documentation that must be completed for drug accountability and return.

# **10.0 ADMINISTRATIVE AND REGULATORY DETAILS**

## **10.1 Confidentiality**

### **10.1.1 Confidentiality of Data**

By signing this protocol, the investigator affirms to the Sponsor that information furnished to the investigator by the Sponsor will be maintained in confidence, and such information will be divulged to the institutional review board, ethics review committee (IRB/ERC) or similar or expert committee; affiliated institution and employees, only under an appropriate understanding of confidentiality with such board or committee, affiliated institution and

employees. Data generated by this trial will be considered confidential by the investigator, except to the extent that it is included in a publication as provided in the Publications section of this protocol.

#### **10.1.2 Confidentiality of Subject Records**

By signing this protocol, the investigator agrees that the Sponsor (or Sponsor representative), IRB/ERC, or regulatory authority representatives may consult and/or copy trial documents in order to verify worksheet/case report form data. By signing the consent form, the subject agrees to this process. If trial documents will be photocopied during the process of verifying worksheet/case report form information, the subject will be identified by unique code only; full names/initials will be masked prior to transmission to the Sponsor.

By signing this protocol, the investigator agrees to treat all subject data used and disclosed in connection with this trial in accordance with all applicable privacy laws, rules and regulations.

#### **10.1.3 Confidentiality of Investigator Information**

By signing this protocol, the investigator recognizes that certain personal identifying information with respect to the investigator, and all subinvestigators and trial site personnel, may be used and disclosed for trial management purposes, as part of a regulatory submissions, and as required by law. This information may include:

1. name, address, telephone number and e-mail address;
2. hospital or clinic address and telephone number;
3. curriculum vitae or other summary of qualifications and credentials; and
4. other professional documentation.

Consistent with the purposes described above, this information may be transmitted to the Sponsor, and subsidiaries, affiliates and agents of the Sponsor, in your country and other countries, including countries that do not have laws protecting such information. Additionally, the investigator's name and business contact information may be included when reporting certain serious adverse events to regulatory authorities or to other investigators. By signing this protocol, the investigator expressly consents to these uses and disclosures.

If this is a multicenter trial, in order to facilitate contact between investigators, the Sponsor may share an investigator's name and contact information with other participating investigators upon request.

#### **10.1.4 Confidentiality of IRB/IEC Information**

The Sponsor is required to record the name and address of each IRB/IEC member that reviews and approves this trial. The Sponsor is also required to document that each IRB/IEC meets regulatory and ICH GCP requirements by requesting and maintaining records of the names and qualifications of the IRB/IEC members and to make these records available for regulatory agency review upon request by those agencies.

### **10.2 Compliance With Financial Disclosure Requirements**

Financial Disclosure requirements are outlined in the US Food and Drug Administration Regulations, Financial Disclosure by Clinical Investigators (21 CFR Part 54). It is the Sponsor's responsibility to determine, based on these regulations, whether a request for Financial Disclosure information is required. It is the investigator's/subinvestigator's responsibility to comply with any such request.

The investigator/subinvestigator(s) agree, if requested by the Sponsor in accordance with 21 CFR Part 54, to provide his/her financial interests in and/or arrangements with the Sponsor to allow for the submission of complete and accurate certification and disclosure statements. The investigator/subinvestigator(s) further agree to provide this information on a Certification/Disclosure Form, commonly known as a financial disclosure form, provided by the Sponsor or through a secure password-protected electronic portal provided by the Sponsor. The investigator/subinvestigator(s) also consent to the transmission of this information to the Sponsor in the United States for these purposes. This may involve the transmission of information to countries that do not have laws protecting personal data.

### **10.3 Compliance With Law, Audit and Debarment**

By signing this protocol, the investigator agrees to conduct the trial in an efficient and diligent manner and in conformance with this protocol; generally accepted standards of Good Clinical Practice (e.g., International Conference on Harmonization of Technical Requirements for Registration of Pharmaceuticals for Human Use Good Clinical Practice: Consolidated Guideline and other generally accepted standards of good clinical practice); and all applicable federal, state and local laws, rules and regulations relating to the conduct of the clinical trial.

The Code of Conduct, a collection of goals and considerations that govern the ethical and scientific conduct of clinical investigations sponsored by Merck, is provided in Section 12.1 - Merck Code of Conduct for Clinical Trials.

The investigator also agrees to allow monitoring, audits, IRB/ERC review and regulatory authority inspection of trial-related documents and procedures and provide for direct access to all trial-related source data and documents.

The investigator agrees not to seek reimbursement from subjects, their insurance providers or from government programs for procedures included as part of the trial reimbursed to the investigator by the Sponsor.

The investigator shall prepare and maintain complete and accurate trial documentation in compliance with Good Clinical Practice standards and applicable federal, state and local laws, rules and regulations; and, for each subject participating in the trial, provide all data, and, upon completion or termination of the clinical trial, submit any other reports to the Sponsor as required by this protocol or as otherwise required pursuant to any agreement with the Sponsor.

Trial documentation will be promptly and fully disclosed to the Sponsor by the investigator upon request and also shall be made available at the trial site upon request for inspection, copying, review and audit at reasonable times by representatives of the Sponsor or any regulatory authorities. The investigator agrees to promptly take any reasonable steps that are requested by the Sponsor as a result of an audit to cure deficiencies in the trial documentation and worksheets/case report forms.

The investigator must maintain copies of all documentation and records relating to the conduct of the trial in compliance with all applicable legal and regulatory requirements. This documentation includes, but is not limited to, the protocol, worksheets/case report forms, advertising for subject participation, adverse event reports, subject source data, correspondence with regulatory authorities and IRBs/ERCs, consent forms, investigator's curricula vitae, monitor visit logs, laboratory reference ranges, laboratory certification or quality control procedures and laboratory director curriculum vitae. By signing this protocol, the investigator agrees that documentation shall be retained until at least 2 years after the last approval of a marketing application in an ICH region or until there are no pending or contemplated marketing applications in an ICH region or until at least 2 years have elapsed since the formal discontinuation of clinical development of the investigational product. Because the clinical development and marketing application process is variable, it is anticipated that the retention period can be up to 15 years or longer after protocol database lock. The Sponsor will determine the minimum retention period and notify the investigator when documents may be destroyed. The sponsor also recognizes that documents may need to be retained for a longer period if required by local regulatory requirements. All trial documents shall be made available if required by relevant regulatory authorities. The investigator must consult with and obtain written approval by the Sponsor prior to discarding trial and/or subject files.

ICH Good Clinical Practice guidelines recommend that the investigator inform the subject's primary physician about the subject's participation in the trial if the subject has a primary physician and if the subject agrees to the primary physician being informed.

The investigator will promptly inform the Sponsor of any regulatory authority inspection conducted for this trial.

Persons debarred from conducting or working on clinical trials by any court or regulatory authority will not be allowed to conduct or work on this Sponsor's trials. The investigator will immediately disclose in writing to the Sponsor if any person who is involved in conducting the trial is debarred or if any proceeding for debarment is pending or, to the best of the investigator's knowledge, threatened.

In the event the Sponsor prematurely terminates a particular trial site, the Sponsor will promptly notify that trial site's IRB/IEC.

According to European legislation, a Sponsor must designate an overall coordinating investigator for a multi-center trial (including multinational). When more than one trial site is open in an EU country, Merck, as the Sponsor, will designate, per country, a national principal coordinator (Protocol CI), responsible for coordinating the work of the principal investigators at the different trial sites in that Member State, according to national regulations. For a single-center trial, the Protocol CI is the principal investigator. In addition, the Sponsor must designate a principal or coordinating investigator to review the trial report that summarizes the trial results and confirm that, to the best of his/her knowledge, the report accurately describes the conduct and results of the trial [Clinical Study Report (CSR) CI]. The Sponsor may consider one or more factors in the selection of the individual to serve as the Protocol CI and or CSR CI (e.g., availability of the CI during the anticipated review process, thorough understanding of clinical trial methods, appropriate enrollment of subject cohort, timely achievement of trial milestones). The Protocol CI must be a participating trial investigator.

